Design: A sample of convenience will be used. Following consent and baseline data collection, participants will be assigned to one of two coaching methods, face to face format or phone. Participants who receive coaching over the phone will follow the exact procedures as face to face except coaching will be provided over the phone. The OPC intervention will last up to 10 weeks. Participants will be involved in the study for up to 18 months including baseline data collection, the intervention, and follow up data collection.

Sample: A convenience sample of up to 20 female primary caregivers, including but not limited to mothers, grandmothers and aunts of children with SCI will be recruited from three facilities specializing in pediatric SCI care and rehabilitation using the following inclusion and exclusion criteria:

Inclusion Criteria

1. Female primary caregivers of children with traumatic or acquired, non-progressive SCI between 6 and 13 years of age
2. Female primary caregivers will have legal guardianship of their child with SCI;
3. Speak, read and comprehend English
4. be available for face-to-face visits at a location in close proximity to the coach who will be providing coaching
5. have a cell phone with text messaging capabilities; be willing to utilize cell phone or land line for coaching
6. be able to verbalize challenges in their own participation or their child's participation during initial screening
7. Provide written consent

Exclusion Criteria

1. Severe mental health condition (female primary caregiver) as documented in the child's medical record or reported to research staff by child's treating physician or medical team member
 - a. If potential participants experience emotional distress, a qualified mental health professional will be available to provide appropriate resources or referrals if needed.
 - b. This would be documented in the child's medical record as standard procedure by the qualified mental health professional
2. Abuses or addictions (female primary caregiver) to illicit or prescribed substances or alcohol at the time of screening as documented in the child's medical record or reported to research staff by the child's treating physician or medical team member
3. Have a child with a diagnosis of suspected conversion syndrome at the time of screening as documented in the child's medical record or reported to research staff by the child's treating physician or medical team member

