4. Have a child who is suicidal at the time of screening as documented in the child's medical or reported to research staff by the child's treating physician or medical team member
 - a. If suicidal ideation (including intent and/or plan) is communicated at any point research staff will connect the participant with the qualified mental health professional who will conduct a suicide risk assessment and if needed, break confidentiality to call emergency personnel.
 - b. This would be documented in the child's medical record as standard procedure by the qualified mental health professional

Facilities: Three facilities specializing in pediatric SCI care and rehabilitation will recruit for and enroll participants in the study 1) Shriners Hospitals for Children- Chicago 2) Shriners Hospitals for Children – Philadelphia and 3) TIRR Memorial Hermann- Houston. Thomas Jefferson University is the regulatory and lead site, however no participants will be enrolled at this site. Each enrolling site will have 1-2 trained coaches who will each recruit, enroll, and complete the study procedures for data collection with up to 5 participants.

Data Collection and Study Procedures:

1. Following consent, screening, and enrollment, baseline data collection will occur including baseline demographics of caregiver and child characteristics, the Beck Anxiety Inventory, the International Spinal Cord Injury Basic Data Set for Primary Caregivers, and the International Spinal Cord Injury Pediatric Activities and Participation Basic Data Set.
2. Each coach will provide the intervention to up to 5 participants. Participants will be assigned to coaching method based on their order of enrollment. Depending on the coach, the first 1-2 participants enrolled will have face to face coaching. The next 1-3 participants will have phone coaching. Seven female primary caregivers will receive the face to face and 9 will receive the phone coaching, for a total of 16 participants to receive the intervention.
3. In the event that face to face is not feasible, participants will have coaching via phone.
4. Caregivers who are have face to face coaching will receive up to 10 coaching sessions at a location that is mutually convenient for the caregiver and coach.
 - a. The caregiver and coach will decide on how the sessions will be distributed over a 10 week period
 - b. All 10 sessions must be completed within a 10 week period
 - c. Each session will not exceed 90 minutes

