 - d. If goals are accomplished before 10 sessions, coaching will cease
 - e. The general content, format and purpose of each coaching session is outlined in Table 1 below.
 - f. All coaching sessions will be audio-recorded for assessment of treatment fidelity
5. Caregivers who are enrolled but who have not started coaching will receive monthly text messages from the project coordinator starting 1 month after enrollment. This is for retaining the participant.
6. The start and stop time of each OPC session will be documented on a study specific CRF that will also include information on caregiver attendance.
7. If coaching sessions are cancelled, rescheduled and/or missed coaches will document the occurrence and the caregivers' reasons for missing the session will be documented.
8. Caregivers who received and finished face to face coaching will be contacted on a monthly basis by the project coordinator via phone and asked about how goal focused problem solving skills have been generalized to other participation challenges and goals. This will be done to keep the caregivers engaged while assessing generalization of skills gained through coaching.
9. Assessments (primary).
 - a. Canadian Occupational Performance Measure: This outcome will evaluate performance of and satisfaction with performance in self-identified goals.

Performance and satisfaction will be rated on a scale between 1-10, where 1 is “cannot perform” “not satisfied” and 10 is “performs without a problem” and “very satisfied”. Goals will be rated by the caregivers before and after coaching.

10. Secondary (exploratory)

- a. Parenting Sense of Competence Scale (PSOC): most widely used measure of parental self-efficacy, it contains 17 items rated on a 6 point scale and evaluates satisfaction with parenting
- b. Parenting Stress Index Short Form-4 (PSI-SF-4): one of the most widely used measures of parental stress, it provides a method to evaluate parent stress with few items. It is comprised of 3 subscales including Parental Distress, Parent-Child Dysfunctional Interaction and Difficult Child as well as a Total Stress Scale.
- c. Pediatric Measure of Participation Short Form (PMoP SF) Parent Report: used to measure a caregiver's perception of their child's participation

11. Satisfaction – following completion of coaching, caregivers will participate in a semi-structured interview to explore satisfaction (Table 2)

Table 1: General Content and Sequence of Coaching Session

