1. Original Site Data: Data will be recorded on standardized or study-specific case report forms. Participants will be assigned a confidential study identifier. The original data and subject identifiers from each site will be kept in a locked file cabinet, accessible only to the key research staff working on the study.
2. Data Transmission from Participating sites to the Lead Site: All data transmitted from the participating site will be de-identified, and coded with a unique subject identifier. Copies of all de-identified measures, CRFs, and audio recordings will be sent to the lead site via secure upload to a study specific Sharefile Account. The PI and/or project coordinator at the lead site will retrieve all data from the Sharefile account and save it to the designated file on the research drive. Once the data of participating sites are saved, they will be permanently removed from the Sharefile account.

Data Handling and Analysis: All data will be recorded on study specific CRFs and standardized measures and assessments. It will be sent to the lead site following the procedure above and will be entered into a study specific database.

Primary Outcome

1. Canadian Occupational Performance Measure: A 2-point change on the COPM indicates a clinically meaningful change, and 0.9 and 1.9 were found to be optimal cut-off points for performance and satisfaction, respectively. We will examine changes in COPM performance and satisfaction scores using non-parametrics.

Secondary Exploratory

2. BIGSS: We will calculate Spearman rank correlation coefficients (r_s) and create a correlation matrix to examine the relationships among caregivers' confidence in achieving goals, goal attainment (COPM), parent competency, stress, anxiety and participation, parent perceptions of child's participation, and caregiver and child characteristics. We will use these associations to better define inclusion and exclusion criteria for a future RCT on OPC, and to define primary and secondary endpoints for a future RCT.

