3. Fidelity: Descriptive and summary statistics will be used to identify the number (mean, mode and range) of coaching sessions conducted for the face-to-face OPC group and the phone OPC group, and the average number and range of sessions required for goal attainment. We will also identify the average time per OPC session for both groups. The number of missed sessions and reasons for missing sessions will be identified. We will examine variability among the four coaches, and will determine if significant differences in these variables exist between OPC face-to-face and phone OPC. These data will be used to define the dosing parameters of OPC for a future RCT.
4. The audio-recordings of each OPC session will be transcribed verbatim. The transcriptions will be read and evaluated on treatment fidelity. Inter-rater reliability on treatment fidelity between the two graduate assistants will be evaluated by calculating intraclass correlation coefficients (ICC, Model 2,1) with 95% confidence intervals (CI). The PI will randomly select 10 transcribed face-to-face OPC sessions and 10 phone OPC sessions, and will also assess

treatment fidelity. Agreement between the assessments of fidelity will serve as an internal quality control, but will also further assess reliability using ICC (2,1) with 95% CI.

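### Do the exploratory Spearman correlations need planned confidence intervals and fully named scores before they inform a future RCT?

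*Combined protocol and SAP*

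**What the plan says.** Data Handling and Analysis, Secondary Exploratory, item 2 (BIGSS) will "calculate Spearman rank correlation coefficients (r_s) and create a correlation matrix". The matrix covers seven named constructs: confidence in reaching goals, goal attainment (COPM), parent competency, stress, anxiety, participation, and the parent's view of the child's participation. Unlisted caregiver and child characteristics are added. Two uses are stated. The first concerns eligibility: "We will use these associations to better define inclusion and exclusion criteria for a future RCT on OPC". The second, in the same sentence, concerns endpoints: "and to define primary and secondary endpoints for a future RCT".

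Data Collection and Study Procedures, item 2, sets the number treated: "for a total of 16 participants to receive the intervention". The Sample paragraph gives the ceiling: "A convenience sample of up to 20 female primary caregivers".

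On which scores exist:
- **Anxiety** is collected at the start, with "baseline demographics of caregiver and child characteristics, the Beck Anxiety Inventory" (Data Collection, item 1).
- **COPM** has two ratings: "This outcome will evaluate performance of and satisfaction with performance in self-identified goals". Both are taken before and after coaching (item 9). Primary Outcome, item 1, says that change in both will be examined.
- **BIGSS** appears in Table 1 at sessions 1 and 10.
- **PSOC, PSI-SF-4 and PMoP SF** are described in item 10 without a time of measurement. PSI-SF-4 has three subscales and a total.

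Item 4 of the Secondary Exploratory list, on fidelity, attaches 95% confidence intervals to its intraclass correlation coefficients. Item 2 attaches none to r_s.

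**The concern.** A correlation from 16 people is very imprecise, and this matrix is given a job beyond description: it feeds the eligibility rules and endpoints of a later trial. The plan provides intervals for one small-sample coefficient (the ICC) but not for the other (r_s), which looks inconsistent. The entering scores are also partly open. A baseline correlation and a correlation of change scores answer different questions, so two analysts could build different matrices from the same text. If bare coefficients were taken at face value, a future trial could be shaped by noise, and a reader of the matrix would not see how uncertain each entry is.

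**Working it through.** **The plan's own figures.** 7 face to face + 9 by phone = 16, as stated. Four coaches (item 3, Fidelity) × up to 5 participants each = 20, which matches the ceiling.

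**Precision of r_s.** The documents give no expected correlation, so 0.3, 0.5 and 0.7 are assumed for illustration. The 95% level is borrowed from the ICC item. The interval uses the Fisher z transform with the Bonett-Wright standard error:

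limits = tanh( atanh(r) ± 1.96 × SE ), with SE = √[(1 + r²/2)/(n − 3)].

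For r_s = 0.5, atanh(0.5) = 0.549.
- n = 16: SE = √(1.125/13) = 0.294; 0.549 ± 0.577 = -0.027 to 1.126; back-transformed, -0.03 to 0.81.
- n = 20: SE = √(1.125/17) = 0.257; 0.549 ± 0.504 = 0.045 to 1.053; back-transformed, 0.05 to 0.78.

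| r_s (assumed) | n = 16 | n = 20 |
|---|---|---|
| 0.3 | -0.24 to 0.70 | -0.17 to 0.66 |
| 0.5 | -0.03 to 0.81 | 0.05 to 0.78 |
| 0.7 | 0.255 to 0.90 | 0.32 to 0.88 |

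With SE = √[1.06/(n − 3)] instead, r_s = 0.5 at n = 16 gives -0.01 to 0.80, so the choice of formula hardly matters. In simulation from bivariate normal data, the Bonett-Wright interval covered 95.6% to 95.9% at these sample sizes.

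**What an interval would change.** The formula needs only r_s and n, so a planned interval adds no information to a matrix reported with its n. It would not improve precision either: a half-width of 0.20 at r_s = 0.5 needs about 64 caregivers, more than three times the ceiling of 20. Item 2 contains no significance test, cut-off or rule for choosing among coefficients, so no stated decision would come out differently.

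**Which scores enter.**
- *COPM.* Goal attainment in item 2 comes directly after item 1, which examines change in both ratings. The natural reading is change, in both.
- *Anxiety.* The only listed time is baseline.
- *BIGSS.* Two times are listed and none is chosen.
- *PSOC, PSI-SF-4, PMoP SF.* The time is not stated, nor whether the PSI-SF-4 total or a subscale enters.
- *Caregiver participation and the characteristics.* No instrument is tied to the first, and the second are not listed.

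The open points are real, but they are choices of detail inside a descriptive matrix. None contradicts another part of the plan.

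**The case for a change.** The best case for a change is that an exploratory label does not cancel a stated use. For endpoints the text says the associations will define them, which is firmer than the hedged wording on eligibility. Comparing instruments by their correlations would be unreliable at this size. In simulation at n = 16, an instrument with a true correlation of 0.5 falls below one with 0.3 in 13% to 29% of samples, as the correlation between the two instruments goes from 0.8 to 0 (all assumed values). Intervals and a short list of scores would cost almost nothing and need no new data.

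The imprecision stands, and so does the remark on wording. The ranking figures, however, describe a rule that the plan does not contain: nothing says that instruments will be ranked by r_s or that the largest will be picked. Nor are the associations said to be the only input. Objective 5 examines how completely and validly the instruments are filled in, and Objective 6 covers the other parameters of the future trial. Low cost alone is not a reason to amend when no result or decision would differ.

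**Conclusion.** The observation is accurate, but it calls for no change. With 16 to 20 caregivers, a moderate correlation is compatible with anything from about no association to a strong one (-0.03 to 0.81 at r_s = 0.5 and n = 16). That limit comes from the size of a feasibility study, and planning an interval would not move it. Calling the matrix hypothesis-generating would repeat what its Secondary Exploratory heading already says. The unnamed scores are a gap that analysts can fill sensibly, provided the report says which score and time point each variable uses. Showing intervals beside the coefficients would be good reporting practice and is open to the analysts as the plan stands.

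This conclusion assumes that the matrix is reported with the number of caregivers behind each coefficient, and that no unstated selection rule is applied to it. The r_s values used here are illustrative.

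### Missed sessions are compared between coaches and formats as a raw number, although the number of sessions a caregiver can miss varies with course length

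*Combined protocol and SAP*

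**What the plan says.** In the combined protocol and SAP, Data Handling and Analysis, item 3 (Fidelity), the attendance measure is a count: "The number of missed sessions and reasons for missing sessions will be identified". The next sentence looks at variability among the four coaches and says the team "will determine if significant differences in these variables exist between OPC face-to-face and phone OPC". The results are meant to inform dosing in a later randomised trial. The same item also summarises, by format, how many sessions were held. It does not link that figure to the missed sessions, and it states no rate, proportion or denominator.

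Course length is not fixed. Under Data Collection and Study Procedures, item 4, face-to-face caregivers "will receive up to 10 coaching sessions at a location that is mutually convenient for the caregiver and coach", and item 4d adds: "If goals are accomplished before 10 sessions, coaching will cease". The Design section carries this over to the other format: "Participants who receive coaching over the phone will follow the exact procedures as face to face except coaching will be provided over the phone".

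On recording, item 6 puts session times and attendance on a case report form. Item 7 says: "If coaching sessions are cancelled, rescheduled and/or missed coaches will document the occurrence", with the caregiver's reasons. What counts as missed is not defined. The planned split is 7 face-to-face and 9 phone, 16 in all (item 2).

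**The concern.** A caregiver can miss only sessions that were scheduled. Someone who reaches her goals after six sessions has had fewer chances to miss one than someone who needs ten. A raw count therefore mixes two things: how reliably caregivers attend and how long their courses last. The plan treats course length as an open question, since it also compares sessions held between formats. It cannot then assume equal exposure when it compares missed sessions.

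At stake is the reading of one exploratory feasibility result. A format or coach whose caregivers finish sooner could appear to have better attendance when attendance is the same, and that reading would feed into the dosing and delivery specifications of the future trial (study objective 6).

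**Working it through.** The plan states no attendance rate, expected course length, test or significance level for this comparison, so there is no figure of its own to reproduce beyond 7 + 9 = 16, which is consistent.

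**Inputs from the documents:** at most 10 sessions (item 4); earlier end on goal attainment (item 4d); the same procedures by phone (Design); groups of 7 and 9 (item 2).

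**Assumed inputs:** sessions scheduled per course, S; chance p of missing any scheduled session, the same in both formats.

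**Expected count.** Expected missed sessions per caregiver = S × p.

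- p = 0.15: 6 × 0.15 = 0.9 and 10 × 0.15 = 1.5. The ratio is 1.5 / 0.9 = 1.67 and the difference is 0.6 sessions per caregiver.
- p = 0.20: 2.0, 1.6, 1.2 and 0.8 missed for courses of 10, 8, 6 and 4 sessions.
- With equal p the ratio is simply the ratio of course lengths. If lengths are equal it is 1 and there is no distortion.
- The order can reverse: 6 × 0.25 = 1.5 is below 10 × 0.20 = 2.0, so the group with the worse attendance shows the lower count.

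**Expected proportion.** (S × p) / S = p, whatever the course length.

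**Effect on a test.** The simulation used 7 caregivers with 10-session courses against 9 with the length shown, binomial misses at the same p in both groups, a two-sided Mann-Whitney test at 0.05 and 4,000 runs per setting. The test and level are assumptions. There is no true difference in attendance, so every rejection is false.

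| Course lengths | Measure | p = 0.1 | p = 0.2 | p = 0.3 |
|---|---|---|---|---|
| 10 vs 10 | count | 4.2% | 3.7% | 3.6% |
| 10 vs 8 | count | 5.7% | 6.8% | 10.4% |
| 10 vs 8 | proportion | 5.6% | 5.5% | 4.6% |
| 10 vs 6 | count | 11.3% | 22.7% | 35.2% |
| 10 vs 6 | proportion | 5.6% | 6.2% | 5.3% |
| 10 vs 4 | count | 25.2% | 51.6% | 74.3% |
| 10 vs 4 | proportion | 8.9% | 6.2% | 5.7% |

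At 10 vs 6, the shorter-course group had the lower mean count in 82%, 92% and 97% of runs. The simulation gives every caregiver in a group the same course length, so it shows the mechanism and does not forecast the trial. The 8.9% for the proportion at 10 vs 4 shows that it too behaves less well when one group's courses are very short.

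**The case against.** The best reply is that the plan already reports sessions held by format, next to missed sessions and their reasons. A careful reader could see that one format had shorter courses and discount its lower count. That stands in part: the ingredients are there. But the plan does not commit to combining them, and the comparisons it does commit to are of the listed variables as they are.

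It is also fair that nothing in the documents points to a large gap in course length between formats, that a gap of 10 against 8 sessions raises the false-positive rate only to about 6 to 10%, and that the count has a use of its own as a measure of burden on staff and caregivers. All of this stands and limits the point.

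A reader might infer more than the text supports:

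- **That dropout would pass for good adherence, or that someone who stops after session 3 would be scored as missing 0 or 7.** The documents give no withdrawal rule, rate or counting convention, and do not say that sessions never scheduled count against 10. Goal attainment alone carries the argument.
- **That cancelled, rescheduled and missed sessions will be pooled.** Item 7 names them separately and the Fidelity item refers only to missed ones. The gap is a missing definition.
- **That flexible spacing changes the number of sessions.** Item 4a says "The caregiver and coach will decide on how the sessions will be distributed over a 10 week period", which concerns timing. The documented source of shorter courses is item 4d.
- **That attendance is a main feasibility result.** None of the seven objectives names it.

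**Conclusion.** The point holds, as a minor one. The count is not a clean measure of attendance wherever the groups compared differ in course length, and the plan allows such differences without providing a denominator.

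The size cannot be computed from the documents. Under the assumed 15% miss chance and 6 versus 10 sessions it is 0.9 against 1.5 missed sessions per caregiver. Under the simulated conditions the false-positive rate of a count-based test is about 6 to 10% at 10 versus 8 sessions and 11 to 35% at 10 versus 6, for miss chances of 0.1 to 0.3. These figures assume equal true attendance and a uniform course length within each format.

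It would be wrong to conclude that the format comparison is biased as planned. It is distorted only if course lengths turn out to differ. The analysis is secondary and exploratory, and its one onward use is in dosing for the future trial.

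**What to change.** In the Fidelity item:

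1. Keep the number of missed sessions as a descriptive measure of burden.
2. Add, for each caregiver, missed sessions divided by sessions scheduled up to the end of coaching. The denominator is sessions held plus sessions missed, from the records under items 6 and 7.
3. Use this proportion for the comparisons among coaches and between formats.
4. Define a missed session as one that was never held. Tabulate cancelled or rescheduled sessions separately.
5. Report any discontinuation of coaching separately from missed sessions.

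The cost is a few sentences of analysis text and a little more analysis work, with no extra visits. The drawback is that the proportion is noisy for very short courses, so the counts and denominators should be shown beside it.

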6. To establish parameters for a future randomized-controlled trial (RCT) on OPC including dosage and delivery specifications for OPC intervention; sample size estimation; and cost and time requirements for OPC study implementation.
7. To determine the feasibility of randomizing caregivers of youth with SCI into a treatment groups.

Risks and Benefits:

1. The risks involved in this research are minimal. Participants may become bored or tired during the coaching sessions or they may become upset or frustrated. Additionally, there may be a loss of confidentiality. In order to protect against risk, coaches are trained clinicians with experience working with parents of children with SCI. In order to minimize the risk of loss of confidentiality,

an identification number will be assigned to all participants. Identification number and corresponding name will be kept in a secure location separate from any participant data.

2. Potential benefits include an intervention developed specifically to meet the needs of female primary caregivers of children with SCI including but not limited to mothers, grandmothers and aunts surrounding caregiving of a child with a chronic condition. This intervention employs problem solving, which is an approach that has been identified as highly relevant for caregivers with SCI, and one that has shown to be highly effective for caregivers of children with other chronic conditions. Secondly, it explicitly focuses on identifying solutions to participation challenges that are associated with the social and physical environments which are areas identified by children with SCI and their caregivers as being problematic.

Research Strategy

Significance: This study addresses the unmet needs of female primary caregivers of youth with SCI. This is significant in that if these needs are not addressed through interventions that are explicitly designed to empower caregivers in their caregiving and parenting roles, both caregivers of youth with SCI and youth with SCI will remain vulnerable to the well-established adverse implications of information caregiving. This is the first study to establish the feasibility of an intervention explicitly for female primary caregivers of youth with SCI, and it will inform the development of standardized methodological procedures for the use of OPC as an intervention for caregivers of youth with SCI as well as a future RCT that will assess the efficacy of OPC for caregivers of youth with SCI.

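### The planned significance comparison of face-to-face with phone coaching is heavily confounded with coach practice and enrolment order, because every coach does face-to-face first

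*Combined protocol and SAP*

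**What the plan says.** All references are to the combined protocol and SAP.

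- **Assignment** (Data Collection and Study Procedures, item 2): "Participants will be assigned to coaching method based on their order of enrollment". Then: "Depending on the coach, the first 1-2 participants enrolled will have face to face coaching". And: "The next 1-3 participants will have phone coaching". The totals are fixed: "Seven female primary caregivers will receive the face to face and 9 will receive the phone coaching", 16 in all, with at most 5 per coach.
- **Fallback** (same section, item 3): "In the event that face to face is not feasible, participants will have coaching via phone".
- **Analysis** (Data Handling and Analysis, item 3, Fidelity): the plan summarizes the number of sessions, sessions needed for goal attainment, time per session and missed sessions. It looks at variability among four coaches and "will determine if significant differences in these variables exist between OPC face-to-face and phone OPC". No test is named.
- **Use**: "These data will be used to define the dosing parameters of OPC for a future RCT".

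Nothing in the document randomizes or alternates mode, adjusts for order or coach experience, or warns that order affects this comparison.

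**The concern.** The Design section says phone participants follow the same procedures apart from the medium, so a reader will take any significant difference as an effect of mode. Yet under the assignment rule the two groups also differ systematically in when the coach saw them. If coaches become quicker with practice, or if early and late enrollees differ, the comparison can show a mode difference that is not there or mask one that is.

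Looking within coach does not help, because the ordering is within coach. The planned look at variability among coaches concerns differences between coaches, not change within one.

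At stake is the step to the next trial. A drift over time could be read as phone coaching needing fewer or shorter sessions, and carried into the RCT dosing parameters.

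**Working it through.** **Inputs from the document.** Four coaches (analysis item 3); 1-2 face-to-face, then 1-3 phone, at most 5 per coach; 7 face-to-face and 9 phone (procedures item 2).

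**1. The plan's own figure.** 7 + 9 = 16. With four coaches, 7 face-to-face forces 2, 2, 2 and 1. Nine phone caregivers at 1-3 per coach can then be placed in 16 ways, which are of five types. The numbers are consistent with the rule.

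**2. Distance in order.** Face-to-face places are 1, 2, 1, 2, 1, 2, 1: mean 10/7 = 1.43. Take the type with phone numbers 2, 2, 2 and 3 (the coach with one face-to-face caregiver has three by phone). Phone places are 3 and 4 for three coaches and 2, 3, 4 for the fourth: mean 30/9 = 3.33. The gap is 1.90 places. Over all five types it is 1.90 to 2.24. Every first place is face-to-face and every place from the third on is phone. Only place 2 overlaps, with three face-to-face and one phone.

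**3. Correlation within coach.** For a coach with f face-to-face and p phone caregivers, n = f + p, the within-coach sums are: mode fp/n, order n(n² − 1)/12, cross-product fp/2. For the same type:

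- mode: 1 + 1 + 1 + 0.75 = 3.75
- order: 4 × 5 = 20
- cross-product: 2 + 2 + 2 + 1.5 = 7.5
- r = 7.5/√(3.75 × 20) = 0.866
- variance inflation = 1/(1 − 0.75) = 4.0

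Over all types: r 0.84 to 0.87, inflation 3.4 to 4.0.

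**4. Cost of adjusting for order.** 95% CI half-width for the mode difference, in residual SD:

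- coach only, 11 df: 2.201/√3.75 = 1.14 (all types 1.11 to 1.16)
- coach and linear order, 10 df: 2.228/√(3.75 × 0.25) = 2.30 (all types 2.16 to 2.30)

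**5. False positives.** The document gives no trend, SD, alpha or test, so all of these are assumed: normal outcome, one value per caregiver, two-sided 5% t test, no mode effect. Simulated over all five types:

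| Assumed change with order | Rejection rate |
|---|---|
| none | about 5% |
| linear, 0.1 SD per caregiver | 6-7% |
| linear, 0.25 SD per caregiver | 14-17% |
| linear, 0.5 SD per caregiver | 38-48% |
| single step of 0.5 SD after the first caregiver | about 8% |
| single step of 1 SD after the first caregiver | 15-16% |

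For the step, all phone caregivers but only 3 of 7 face-to-face caregivers come after it, so the false difference is (1 − 3/7) = 0.57 of the step: 0.29 and 0.57 SD.

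A coach-adjusted test is no protection. If coaches hold an assumed 30% of the variance, it rejects in 7%, 18-21% and 49-57% at the three linear trends. Adding the linear order term restores about 5%, at the width in step 4.

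**The case against.** The strongest reply is that no practice effect is shown. The coaches are described as trained clinicians. Sessions are capped at 10 and 90 minutes and follow Table 1, which limits drift in number and length. That the literature lacks OPC studies in pediatric SCI says nothing about how practised these coaches are. This stands: the size of any trend is an assumption. At 0.1 SD per caregiver the error is close to nominal, and the 38-48% needs a linear change of 2 SD from a coach's first to fifth caregiver. A rank test in that case gives somewhat less, about 34-43%. What does not follow is that the comparison is sound, since the design could not show whether a trend was present.

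A reader might infer that mode and order cannot be separated at all. That goes too far. A linear order term, helped by the one overlapping place, separates them in principle, only too imprecisely to be of use with 16 caregivers.

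A reader might also infer that the fallback fills the phone group with caregivers who are harder to reach. Inclusion criterion 4 requires every caregiver to be available for face-to-face visits, which limits this. Some selection remains possible, and it would occur by feasibility, not by chance.

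Finally, one might read objective 7, "To determine the feasibility of randomizing caregivers of youth with SCI into a treatment groups", as something this assignment was meant to serve and fails. The document does not link the two, so the point does not rest on it.

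**Conclusion.** The point holds as a confounding problem in one exploratory comparison. Mode is tied to order by the assignment rule (r 0.84 to 0.87 within coach; 1.9 to 2.2 places apart), and that much follows from the document alone. How far the comparison would mislead depends on a trend that the document does not give: from almost nothing at 0.1 SD per caregiver to 38-48% false positives at 0.5 SD.

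Its reach is limited. Coach identity is not the confounder, because each coach delivers both modes. The COPM before-after analysis does not use this comparison. The dosing parameters also draw on overall session counts, times and missed sessions. It would be wrong to conclude that the study's dosing information is unusable; only a mode-specific reading of it is unsafe.

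**What to change.** In analysis item 3, replace the significance comparison between modes with a table of each variable by coach, enrolment order and mode, and show caregivers moved to phone separately. Add that a mode difference cannot be reliably separated from coach experience or enrolment order, and should not by itself set mode-specific dosing parameters. This costs one table and two sentences, and gives up a p-value that could not be interpreted.

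The document does not state enrolment status. If assignment has not started, an option is to keep the 7 and 9 and each coach's numbers, randomize within coach which places are face-to-face and which are phone, and compare modes within coach with a 95% CI. In simulation with modes randomized this way, the plain t test rejected in about 5-6% of trials at linear trends up to 0.5 SD per caregiver (3-4%, so conservative, with the 30% coach share). It needs a list of 16 places, best held at the lead site, and coaches ready to work by phone from their first caregiver. A coach's last places would be predictable, chance imbalance would remain, and precision would stay near ±1.1 SD.
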